Coagulation ^d	X	X								Specific analytes are listed in Appendix 1 . PT/INR will be tested at Screening, Week 0, and if significant abnormal liver function tests are observed.
Fasting Lipid Profile ^d		X			X		X	X		Specific analytes are listed in Appendix 1 .
Serology	X									Includes HBsAg, anti-HCV, and anti-HIV.

	Screening	Treatment Period ^a						ET ^b	Follow-Up ^c	Notes
Visit	Screening	Week 0	Week 2	Week 4	Week 6	Week 8	Week 12		Week 16	
Study Day	-42 to Day -1	Day 1	15	29	43	57	85		113	Visit windows post-randomization through Week 12: \pm 3 days from the specified study day. Visit window Week 16: 1 week prior/+2 days from the specified study day.
COVID-19 Assessment ^{d,e}	X	X			X		X			Screening and on-study COVID-19 assessments should be conducted in accordance with Appendix 8 .
Serum pregnancy test ^d	X	X		X		X	X	X		WOCBP only.
Serum FSH	X									To confirm postmenopausal status, as outlined in Appendix 7 .
Blood Alcohol Test	X									
Urinalysis ^d	X	X			X		X	X	X	Specific analytes are listed in Appendix 1 . Microscopic examination is required if blood or protein is abnormal.
Urine Drug Screen ^d	X	X		X		X	X	X	X	
Total Urine Collection (PK/PD Sub-Study only)		X			X					Total urine collection from 0-8 hours post dose as specified in Appendix 2 .
Intensive PK and PD Sampling (PK/PD Sub-Study only)		X			X		X			Intensive PK sampling will be performed pre-dose and 0.5, 1, 2, 4, 6, 8 and 24 hours after the first dose of study drug on Week 0/Day 1 and Week 6, and at pre-dose and 0.5, 1, 2, 4, 6, 8, 24, 48 and 72 hours after the last dose of study drug at Week 12. Refer to Appendix 2 for additional detail.

	Screening	Treatment Period ^a						ET ^b	Follow-Up ^c	Notes
Visit	Screening	Week 0	Week 2	Week 4	Week 6	Week 8	Week 12		Week 16	
Study Day	-42 to Day -1	Day 1	15	29	43	57	85		113	Visit windows post-randomization through Week 12: \pm 3 days from the specified study day. Visit window Week 16: 1 week prior/+2 days from the specified study day.
Trough PK and PD Sampling ^d		X	X	X	X	X	X	X		Only one sample will be collected at each visit prior to drug administration on the visit day. Patients discontinuing the study at any time for any reason will have one sample collected at the ET visit. Refer to Appendix 2 for additional detail.
Baseline sVAP-1 ^f		X								
NASH/Fibrosis Biomarkers ^d		X			X		X	X		Includes CK-18 (M30 and M65), PIIINP, TIMP-1, HA, PRO-C3, and C3M.
Inflammation Biomarkers ^d		X	X	X	X	X	X	X		Includes hs-CRP, IL-6, ICAM-1, and VCAM-1.

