Appendix 2: Sample Collection for Pharmacokinetics and Pharmacodynamics

[Table 3](#) presents a description of PK/PD sample requirements at each study visit and timepoint.

Table 3 PK/PD Sampling Timepoints

Week	Day	Timepoint
0 ¹	1	
• Pre-dose (All Patients)• Post dose at the following timepoints (PK/PD sub-study only):
○ 30 ± 2 minutes○ 1 hour ± 5 minutes○ 2 hours ± 5 minutes○ 4 hours ± 15 minutes○ 6 hours ± 15 minutes○ 8 hours ± 30 minutes• Total urine collection from 0-8 hours post dose (PK/PD sub-study only)
0	2	
• Post Day 1 dose at the following timepoint (PK/PD sub-study only):
○ 24 hours ± 1 hour
2	15 ± 3	
• Pre-dose (All Patients)
4	29 ± 3	
• Pre-dose (All Patients)
6	43 ± 3	
• Pre-dose (All Patients)• Post dose at the following timepoints (PK/PD sub-study only):
○ 30 ± 2 minutes○ 1 hour ± 5 minutes○ 2 hours ± 5 minutes○ 4 hours ± 15 minutes○ 6 hours ± 15 minutes○ 8 hours ± 30 minutes• Total urine collection from 0-8 hours post dose (PK/PD sub-study only)
6	44	
• Post Week 6 dose at the following timepoint (PK/PD sub-study only):
○ 24 hours ± 1 hour
8	57 ± 3	
• Pre-dose (All Patients)

Week	Day	Timepoint
12	85 ± 3	
• Pre-dose (All Patients)• Post dose at the following timepoints (PK/PD sub-study only):
○ 30 ± 2 minutes○ 1 hour ± 5 minutes○ 2 hours ± 5 minutes○ 4 hours ± 15 minutes○ 6 hours ± 15 minutes○ 8 hours ± 30 minutes
12	86	
• Post Week 12 dose at the following timepoint (PK/PD sub-study only):
○ 24 hours ± 1 hour
12	87	
• Post Week 12 dose at the following timepoint (PK/PD sub-study only):
○ 48 hours ± 2 hours
12	88	
• Post Week 12 dose at the following timepoint (PK/PD sub-study only):
○ 72 hours ± 4 hours
ET	ET	
• At the ET Visit, for all patients discontinuing the study at any time for any reason prior to Week 12

NOTES:

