### 8.7.4. Plasma Pharmacokinetic Parameters

Sparse PK samples may be used to calculate PK parameters using population pharmacokinetic (Pop PK) modeling. Data from the study may be combined with data from other studies for the

purposes of Pop PK modeling. If Pop PK modeling is performed, the process will be described in a separate analysis plan.

For the purposes of this SAP, plasma PK parameters will be computed for the PK/PD sub-study patients only. Plasma PK parameters for TERN-201 and its metabolites (TRN-001021 and TRN-001744) will be calculated from the individual plasma concentrations using a non-compartmental approach for Week 0/Day 1, Week 6, and Week 12. Week 0/Day 1 and Week 6 will include pre dose and all post dose assessments prior to the next dose. Week 12 will include pre dose and all post dose assessments. The actual PK sampling times will be used for the PK analysis. If actual PK sampling times are missing, nominal times will be used. If the 24 hr sample is missing at Week 6 or Week 12, the predose sample concentration may be re-used for the 24 hr sample for the purposes of calculating PK parameters, if appropriate.

**Table 6** presents the plasma PK parameters for TERN-201 and its metabolites (TRN-001021 and TRN-001744) to be calculated.

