**Table 6: Plasma Pharmacokinetic Parameters**

Abbreviation	Parameter Definition
AUC 0-∞	For Week 0/Day 1 only, area under the drug concentration-time curve from time zero to infinity, calculated using the linear trapezoidal rule for increasing concentrations and the logarithmic rule for decreasing concentrations as $AUC_{0-tlast} + C_t / \lambda_z$ .
%AUC extrap	For Week 0/Day 1 only, percentage of AUC that is due to extrapolation from the last measurable concentration to infinity
AUC 0-t	For Week 0/Day 1 only, area under the plasma concentration curve over from time 0 to time t, i.e. from 0 to 24 hours, calculated using the linear trapezoidal rule for increasing concentrations and the logarithmic rule for decreasing concentrations.
AUC 0-8hr	For Week 0/Day 1 and Week 6, area under the plasma concentration curve over from time 0 to 8 hours, calculated using the linear trapezoidal rule for increasing concentrations and the logarithmic rule for decreasing concentrations.
AUC tau	For Week 6 and Week 12, area under the plasma concentration curve over a dosing interval, i.e. from 0 to 24 hours, calculated using the linear trapezoidal rule for increasing concentrations and the logarithmic rule for decreasing concentrations.
C max	Maximum observed plasma concentration, obtained directly from the plasma concentration-time profiles within the sampling interval, i.e. calculated for each intensive sampling visit separately (Week 0/Day 1, Week 6, Week 12). In the case where multiple peaks are of equal magnitude, the earliest peak concentration will be reported as C max .
C min	Minimum observed plasma concentration, obtained directly from the plasma concentration-time profiles at steady state, within the sampling interval, i.e. calculated for each intensive sampling visit separately (Week 6 Week 12). In the case where multiple minimums are of equal magnitude, the latest minimum concentration will be reported as C min .

Abbreviation	Parameter Definition
T max	Time of the maximum observed plasma concentration, obtained directly from the plasma concentration-time profiles within the sampling interval, i.e. calculated for each intensive sampling visit separately (Week 0/Day 1, Week 6, Week 12). In the case where multiple peaks are of equal magnitude, the time of the earliest peak will be reported as the t max .

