### 8.8.4. Plasma PD Parameters

Plasma PD parameters will be computed for PK/PD sub-study patients only. Plasma PD parameters for plasma VAP-1/SSAO activity and methylamine will be calculated from the individual plasma VAP-1/SSAO activities and methylamine concentrations using a non-compartmental approach for Week 0/Day 1, Week 6, and Week 12. Week 0/Day 1 and Week 6 will include pre-dose and all post dose assessments prior to the next dose. Week 12 will include pre dose and all post dose assessments. The actual PD sampling times will be used for the PD analysis. If actual PD sampling times are missing, nominal times will be used.

[Table 8](#) and [Table 9](#) present the plasma PD parameters to be calculated.

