**Table 8: VAP-1/SSAO Plasma PD Parameters**

Abbreviation	Parameter Definition
AAUC tau	Area under curve for VAP-1/SSAO activity, calculated separately for the value, change from baseline, and percent change from baseline over a dosing interval, i.e. from 0 to 24 hours, calculated using the linear trapezoidal rule.

Abbreviation	Parameter Definition
$A_{\min}$	Minimum observed VAP-1/SSAO activity, calculated separately for the value, change from baseline, and percent change from baseline, obtained directly from the plasma VAP-1/SSAO activity time profiles. In the case where multiple minimums are of equal magnitude, the earliest minimum values will be reported as $A_{\min}$ .
$A_{\max}$	Maximum observed VAP-1/SSAO activity, calculated separately for the value, change from baseline, and percent change from baseline, obtained directly from the plasma VAP-1/SSAO activity time profiles. In the case where multiple maximums are of equal magnitude, the earliest maximum values will be reported as $A_{\max}$ .
$AT_{\min}$	Time of the minimum observed VAP-1/SSAO activity, calculated separately for the value, change from baseline, and percent change from baseline, obtained directly from the plasma VAP-1/SSAO activity time profiles. In the case where multiple minimums are of equal magnitude, the time of the earliest minimum will be reported as the $AT_{\min}$ .
$AT_{\max}$	Time of the maximum observed VAP-1/SSAO activity (and separately, change and percent change from baseline), obtained directly from the plasma VAP-1/SSAO activity and methylamine concentration-time profiles. In the case where multiple maximums are of equal magnitude, the time of the earliest maximums will be reported as the $AT_{\max}$ .
$AT_{\text{last}}$	Time of the last quantifiable VAP-1/SSAO activity value
$A_{\text{avg}}$	Average observed VAP-1/SSAO activity, calculated separately for the value, change from baseline, and percent change from baseline at steady state (Week 6 and Week 12 only)

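### Week 12 PK minima, some PD extremes and the averages have no 0–24 h limit, so they can take in samples drawn 48 and 72 h after the last dose

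*SAP*

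**What the plan says.** - **Sampling.** Protocol 1.3 and Appendix 2 schedule the Week 12 intensive samples at pre-dose and "0.5, 1, 2, 4, 6, 8, 24, 48 and 72 hours after the last dose of study drug at Week 12". The Week 6 series ends with the 24 h sample. That is ten samples against eight.
- **Which samples enter the profile.** For PK, SAP 8.7.4 says "Week 0/Day 1 and Week 6 will include pre dose and all post dose assessments prior to the next dose", followed by "Week 12 will include pre dose and all post dose assessments". SAP 8.8.4 repeats both rules for PD: "Week 0/Day 1 and Week 6 will include pre-dose and all post dose assessments prior to the next dose", with no cut at Week 12.
- **PK parameters (Table 6).** Cmin is the "Minimum observed plasma concentration, obtained directly from the plasma concentration-time profiles at steady state, within the sampling interval", and that interval is then explained as each intensive sampling visit. Tmin has the same window and takes the latest minimum. Cavg is a steady-state average with no interval. AUCtau and Ctau are tied to the 24 h dosing interval.
- **PD parameters (Tables 8 and 9).** Amax is the "Maximum observed VAP-1/SSAO activity, calculated separately for the value, change from baseline, and percent change from baseline", read from the activity profile with no time limit. The other PD minima, maxima and their times are defined in the same way. Aavg and methylamine Cavg are steady-state averages with no interval. Only the PD areas are limited to 0–24 h.
- **Values below quantification (BLQ).** For PK, values after a measurable concentration are set to missing, and those before the first measurable one are set to zero (8.7.1, 8.7.3). For PD, they are set to half the limit (8.8.1).
- **Use.** Aavg, Amin, methylamine Cavg and methylamine Cmax enter the ANCOVA at Week 12 (8.8.4.3) and the dose-response comparisons (8.8.4.4). Exposure-response uses AUCtau, Cmax and Ctau (8.9).

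**The concern.** A sample taken 48 or 72 h after the last dose of a once-daily drug lies outside any dosing interval. A minimum found there is not a steady-state minimum. A maximum of enzyme activity found there describes recovery after stopping, not the weakest suppression on treatment.

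Table 6 separates a dosing interval (for AUCtau) from a sampling interval (for Cmin and Tmin). A programmer following the text would therefore search the Week 12 profile to 72 h and the Week 6 profile to 24 h. Lower Cmin or higher Amax at Week 12 could then be read as loss of exposure or of target suppression when nothing but withdrawal has occurred.

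Plasma PK parameters are a secondary endpoint, and Aavg is derived from the activity measure behind the other secondary endpoint.

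**Working it through.** The documents give no value for any of these parameters, so there is no figure to reproduce. They also give no half-life, assay limit or enzyme turnover rate. Protocol 2.2.2 says only that the drug is cleared rapidly and that half-life rises with dose. The ranges below are assumptions.

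**PK Cmin and Tmin.** Assume a one-compartment oral model at steady state, with absorption rate 1.5/h, half-life 3 to 48 h and a lower limit of quantification (LLOQ) of 0.1% to 5% of Cmax. Use the protocol's sampling times and the SAP's BLQ rule. Once absorption is over, C(72 h)/C(24 h) = 2^(−48/t½):

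- 12 h: 2^(−4) = 0.0625
- 24 h: 2^(−2) = 0.25
- 48 h: 2^(−1) = 0.50

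With the BLQ rule applied:

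| t½ (h) | LLOQ, % of Cmax | Week 6 Cmin, % of Cmax (time) | Week 12 Cmin, % of Cmax (time) | Ratio |
|---|---|---|---|---|
| 3 | 0.1 | 0.67 (24 h) | 0.67 (24 h) | 1.00 |
| 3 | 1 or 5 | 0 (pre-dose) | 0 (pre-dose) | none |
| 6 | 0.1 | 8.4 (24 h) | 0.52 (48 h) | 0.06 |
| 6 | 1 or 5 | 8.4 (24 h) | 8.4 (24 h) | 1.00 |
| 12 | 0.1 or 1 | 29.3 (24 h) | 1.83 (72 h) | 0.06 |
| 12 | 5 | 29.3 (24 h) | 7.3 (48 h) | 0.25 |
| 24 | 0.1 to 5 | 54.4 (24 h) | 13.6 (72 h) | 0.25 |
| 48 | 0.1 to 5 | 73.9 (24 h) | 36.9 (72 h) | 0.50 |

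The distortion therefore needs a quantifiable 48 or 72 h sample. The 24 h concentration, which is Ctau, has a ratio of 1.00 in every row.

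**VAP-1/SSAO activity.** The protocol describes an irreversible inhibitor, so assume each dose cuts activity to a fraction s of its pre-dose value by 2 h. Activity then recovers by resynthesis with half-life T:

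A(t) = 1 − (1 − Am) × 2^(−(t−2)/T), with Am = s × A0.

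At steady state A0 = A(24), so A0 = (1 − e)/(1 − s × e), where e = 2^(−22/T).

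For T = 48 h and s = 0.10:

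- e = 0.728 and A0 = 0.272/0.927 = 0.294
- Am = 0.029
- A(72) = 1 − 0.971 × 2^(−70/48) = 1 − 0.971 × 0.364 = 0.647
- Amax ratio, Week 12 to Week 6: 0.647/0.294 = 2.20

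Results for s = 0.10, in % of baseline, Week 6 → Week 12:

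| T (h) | Amin | Amax | Amax ratio | Aavg, area/interval | Aavg, mean of samples |
|---|---|---|---|---|---|
| 24 | 4.97 → 4.97 | 49.7 → 87.4 | 1.76 | 28.1 → 57.2 | 24.2 → 35.6 |
| 48 | 2.94 → 2.94 | 29.4 → 64.7 | 2.20 | 16.2 → 37.8 | 14.1 → 22.7 |
| 96 | 1.61 → 1.61 | 16.1 → 40.6 | 2.52 | 8.8 → 22.2 | 7.6 → 13.1 |
| 168 | 0.95 → 0.95 | 9.5 → 25.8 | 2.72 | 5.2 → 13.6 | 4.5 → 8.0 |

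For T of 48 to 168 h, Amax rises 2.2- to 2.7-fold. Adding T = 24 h and s = 0.02 widens the range to 1.8- to 2.9-fold. ATmax moves from pre-dose to 72 h. The Aavg columns show what happens if the average is taken over the whole Week 12 profile, which the SAP neither requires nor excludes.

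Methylamine was not modelled. It rises under inhibition, so by direction of effect its off-drug fall would reach Cmin and Tmin and should leave Cmax nearly unchanged.

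With every parameter restricted to 0–24 h, the Week 12/Week 6 ratio is 1.00 under true steady state for all assumed values (where Cmin is not zero).

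**The case against.** The SAP sentence on Week 12 only says which samples enter the noncompartmental analysis, and the late samples do belong there for the terminal phase. A pharmacokineticist may read the steady-state label on Cmin, Tmin and the averages as excluding off-drug samples. That reading is possible, but the label sits beside a window explained as the sampling visit, in a table that uses 0–24 h where it means it. The text needs to be settled.

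Several limits on the effect stand:

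- A reader might infer that Week 12 Cmin must collapse. It need not. If both late samples are BLQ they are set to missing, and Cmin falls back to the 0–24 h value. Rapid clearance makes this plausible.
- A reader might infer that all PD extremes become washout values. Amin does not change and methylamine Cmax should change little, and these are the only two extremes in the ANCOVA.
- A reader might compare 72 h activity with a flat residual of about 5% and infer a 4- to 10-fold rise. That ignores recovery between doses, which already lifts the on-treatment maximum.
- No Week 6 versus Week 12 test of Cmin or Amax is planned. These are descriptive, in about 8 active patients in Part 1 and 6 per dose in Part 2 (SAP 2.2), and all testing is nominal (8.6).
- Values at 48 and 72 h already appear in the by-timepoint summaries, and a Tmin of 72 h reveals itself.

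Two things are left unanswered. The BLQ rule gives PD no comparable protection, because activity that is recovering moves away from the limit. And Aavg and methylamine Cavg are tested at Week 12 without an averaging interval. SAP 8.8.4.3 calls them pre-dose or trough values, which does not define one.

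**Conclusion.** The point holds as a gap in definition with limited reach. Followed literally, the SAP can report off-drug values as Week 12 steady-state Cmin and Tmin, and as Week 12 Amax, ATmax and methylamine Cmin and Tmin. It also leaves the interval for Cavg, Aavg and methylamine Cavg open.

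The size depends on quantities the documents do not give. For Cmin it runs from no distortion, through a 2-fold understatement (half-life 48 h), to 16-fold (1/0.0625, half-life 12 h with 72 h quantifiable). Because half-life rises with dose, late samples may be quantifiable more often at higher doses, so the distortion could differ between dose groups. For Amax the assumed model gives roughly a doubling to near-tripling.

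The documents do not support a broader claim that Week 12 exposure or suppression results as a whole are invalid. AUCtau, Ctau, CLss/F and the AUC accumulation ratio are fixed to 24 h. Cmax should fall early after the dose, so the exposure-response inputs should remain sound. The secondary PD endpoint itself is analysed by time point (SAP 8.8.3), not through these extremes. The change is still worth making, mainly for the tested averages and for the comparability of Cmin.

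**What to change.** - In SAP Tables 6, 8 and 9, define Cmin, Tmin, Cavg and all PD minimum, maximum, time-of-extreme and average parameters over the 0–24 h dosing interval at both Week 6 and Week 12.
- Say how Cavg, Aavg and methylamine Cavg are computed: area divided by 24 h, or mean of samples.
- In 8.7.4 and 8.8.4, state that the Week 12 samples at 48 and 72 h are used only for λz, t½ and the time of the last quantifiable value.
- Label activity and methylamine at 48 and 72 h as off-drug recovery in the existing by-timepoint summaries.

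This costs a few lines of SAP text and one programming filter. It needs no new data or visits. If 0–24 h was always intended, the change only records it.

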Plasma exposures to TERN-201 were greater than dose proportional. TERN-201 was rapidly cleared from plasma. Steady state was achieved in the highest dose group (10 mg) after Day 7 of dosing. The half-life of TERN-201 increased with dose, suggesting saturable, target-mediated clearance.

Single and multiple doses of TERN-201 significantly suppressed plasma total amine oxidase activity at all doses studied. Using an exploratory assay to assess the effect of TERN-201 on VAP-1/SSAO-specific amine oxidase activity in the plasma, near complete inhibition (>80% with 1 mg, > 90% with 10 mg) was observed after only a single dose on Day 1 (achieved within 4 hours after dosing) with sustained suppression over the dosing period in MAD cohorts. Dose-dependent increases in methylamine, an endogenous substrate of VAP-1/SSAO predicted to increase upon VAP-1/SSAO inhibition, were observed after the first dose of TERN-201 and continued to increase in a dose-dependent manner after multiple doses of TERN-201.

Based on the exploratory assessment on plasma PK of two TERN-201 metabolites, TRN-001021 and TRN-001744, the percentages of either metabolite AUC relative to the total TERN-201-related plasma AUC (sum of TERN-201, TRN-001021, and TRN-001744) were calculated. Median TRN-001021 AUC was <10% and 13.7% of the total plasma AUC associated with TERN-201 in the 4 mg and 10 mg groups, respectively. Median TRN-001744 AUC was 11.5% and <10% of the total plasma AUC associated with TERN-201 in the 4 mg and 10 mg groups, respectively.

Additional details on Study TERN201-US-A101 are available in the Investigator's Brochure.

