MAD	Multiple ascending dose
MCH	Mean corpuscular hemoglobin
MCHC	Mean corpuscular hemoglobin concentration
MCV	Mean corpuscular volume
MedDRA	Medical Dictionary for Regulatory Activities
MMRM	Mixed model for repeated measures
MRI	Magnetic Resonance Imaging
MRI-PDFF	Magnetic Resonance Imaging Proton Density Fat Fraction
mRNA	Messenger RNA
MTD	Maximum tolerated dose
NAFLD	Nonalcoholic fatty liver disease
NASH	Nonalcoholic Steatohepatitis
NCI	National Cancer Institute
NFS	NAFLD fibrosis score
NIMP	Noninvestigational medicinal product
NOAEL	No observed adverse effect level
PCR	Polymerase chain reaction
PD	Pharmacodynamic(s)
PIIINP	Procollagen III N-terminal propeptide
PK	Pharmacokinetic(s)
po	Per os (oral)
PP	Per protocol
PPV	Positive predictive value
PRO-C3	Pro-peptide of type III collagen
PT	Prothrombin time
PTZ	Pentylenetetrazole
QD	Once daily
RBC	Red blood cell
RNA	Ribonucleic acid
SAD	Single ascending dose
SAE	Serious adverse event

Abbreviation or special term	Explanation
SAP	Statistical analysis plan
SARS-COV-2	Severe Acute Respiratory Syndrome Coronavirus 2
SCr	Standardized serum creatinine
SSAO	Semicarbazide-sensitive amine oxidase
SUSAR	Suspected unexpected serious adverse reactions
TEAE	Treatment emergent adverse event
TERN-201	An investigational selective VAP-1/SSAO inhibitor; a.k.a., LSN3415221 (LSN3379274·TsOH), LSN3394258 (LSN3379274·2HCl) and LSN3379274 (free base))
THC	Tetrahydrocannabinol
TIMP-1	Tissue inhibitor of metalloproteinases-1
TRN-001021	O-demethylation metabolite of TERN-201
TRN-001744	O-dealkylation metabolite of TERN-201
UACR	Urine albumin:creatinine
ULN	Upper limit of normal
UPCR	Urine protein: creatinine
US	United States
VAP-1	Vascular Adhesion Protein-1
VCAM-1	Vascular cell adhesion molecule-1
VLDL	Very low-density lipoprotein
WBC	White blood cell
WOCBP	Women of childbearing potential

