## **8.7. Pharmacokinetic (PK) Analyses**

Analyses of trough PK concentrations will use the PK Analysis Set. Analyses of intensive PK concentrations and PK parameters will use the PK/PD Substudy Analysis Set. All PK endpoints, recorded and derived, will be presented in by-patient data listings.

Plasma and urine TERN-201 and metabolite (TRN-001021 and TRN-001744) concentrations will be used as supplied by the analytical laboratory for PK analysis. The units of concentration and resulting PK parameters, with amount or concentration in the unit, will be presented as they are received from the analytical laboratory, with the exception of metabolite to parent ratios which will be corrected for differences in molecular weight. Urine volume will be presented with urine concentrations. Urine collection dates and times from the EDC will be used for analyses, otherwise plasma collection dates and times from the central vendor will be used.

Blood and urine samples will be collected at the timepoints specified in Appendix 2 of the study protocol.

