T min	Time of the minimum observed plasma concentration, obtained directly from the plasma concentration-time profiles at steady state, within the sampling interval, i.e. calculated for each intensive sampling visit separately (Week 6 Week 12). In the case where multiple minimum are of equal magnitude, the time of the latest minimum will be reported as T min .
T last	Time of the last quantifiable plasma concentration, obtained directly from the plasma concentration-time profiles within the sampling interval, i.e. calculated for each intensive sampling visit separately (Week 0/Day 1, Week 6, Week 12).
t 1/2	Apparent plasma terminal elimination half-life, calculated as $\ln(2) / \lambda_z$ .
CL/F	Apparent total plasma clearance calculated as Dose / AUC 0-∞ for Week 0/Day 1
CL ss /F	Apparent total plasma clearance at steady state, calculated as Dose / AUC τau for Week 6 and Week 12.
V z /F	Apparent volume of distribution, calculated as Dose / ( $\lambda_z * AUC_{0-∞}$ ) for Week 0/Day 1
V ss /F	Apparent volume of distribution, calculated as Dose / ( $\lambda_z * AUC_{τau}$ ) for Week 6 and Week 12.
RA AUCτau	Observed accumulation ratio based on AUC τau calculated as AUC τau (Week 6 and Week 12) / AUC 0-24hr (Day 1).
RA Cmax	Observed accumulation ratio based on C max , calculated as C max (Week 6 and Week 12) / C max (Day 1).
LR	Linearity ratio calculated as AUC τau (Week 6 and Week 12) / AUC 0-∞ (Day 1)
C avg	Average observed drug concentration at steady state (Week 6 and Week 12 only)
C 24	For Week 0/Day 1, observed drug concentration at the end of the dosing interval, e.g. from 0 to 24 hours
C τau	Observed drug concentration at the end of the dosing interval, e.g. from 0 to 24 hours (Week 6 and Week 12 only)
λ z	Apparent terminal rate constant (listed only)

In addition, the metabolite-to-parent ratios will be calculated for AUCτau, Cτau, and Cmax. Metabolite-to-parent ratios will be corrected for molecular weight differences by multiplying the ratio by a correction factor. The correction factor for TRN-001021 ratios is 1.05 and the correction factor for TRN-001744 ratios is 1.42.

Additional PK parameters may be determined where appropriate.

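### SAP Table 6 computes CL/F, CLss/F, Vz/F and Vss/F for the two metabolites from the TERN-201 dose, so those values are confounded with the unknown fraction formed and mislabelled

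*SAP*

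**What the plan says.** SAP 8.7.4 covers three analytes, TERN-201, TRN-001021 and TRN-001744. Their plasma parameters "will be calculated from the individual plasma concentrations using a non-compartmental approach for Week 0/Day 1, Week 6, and Week 12", and Table 6 "presents the plasma PK parameters for TERN-201 and its metabolites (TRN-001021 and TRN-001744) to be calculated".

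Table 6 then defines:

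- CL/F (Week 0/Day 1): "Apparent total plasma clearance calculated as Dose / AUC" to infinity.
- CLss/F (Weeks 6 and 12): "Apparent total plasma clearance at steady state, calculated as Dose / AUC" over the dosing interval.
- Vz/F and Vss/F: "Apparent volume of distribution, calculated as Dose" divided by the product of the terminal rate constant and the corresponding AUC.

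Some rows are restricted by visit, and the terminal rate constant is marked as listed only. No row is restricted by analyte. SAP 8.7.4.3 makes reporting depend on the terminal-phase fit and flags heavily extrapolated values. SAP 8.7.5 summarises the parameters by treatment group. Neither exempts the metabolites. The molecular-weight correction in SAP 8.7 applies to ratios only: units are kept as received "with the exception of metabolite to parent ratios which will be corrected for differences in molecular weight".

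**The concern.** Both metabolites are formed in the body. Protocol Appendix 9 describes TRN-001021 as the "O-demethylation metabolite of TERN-201" and TRN-001744 as its O-dealkylation metabolite. Nobody is dosed with either, so the amount of metabolite entering the circulation is unknown. Dividing the parent dose by a metabolite AUC mixes how much metabolite is formed with how fast it is cleared.

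A metabolite with low exposure because little is formed would appear in the table with a high clearance. If formation changes with dose, the tabulated value changes too, and a reader could take this for a change in elimination. That is plausible here, because Protocol 2.2.2 reports exposure rising more than in proportion to dose and suggests saturable clearance.

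**Working it through.** The plan states no metabolite clearance or volume, so there is no figure to reproduce. The check has four steps.

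**1. What the formula returns.** Let F·fm be the fraction of the administered dose that reaches the circulation as metabolite. In molar units, amount formed equals amount cleared:

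AUC_m = F·fm·Dose / CL_m, so Dose/AUC_m = CL_m/(F·fm).

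This equals CL_m only if F·fm = 1. Likewise Dose/(λz·AUC_m) = CL_m/(F·fm·λz). That equals V_m/(F·fm) only if λz is the metabolite's own rate constant, CL_m/V_m.

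**2. Numerical check.** A linear parent-metabolite model was integrated with assumed values, none from the documents: F = 1, ka = 1/h, CL_p = 20 L/h, V_p = 60 L, CL_m = 20 L/h, V_m = 50 L. The slowest rate is the parent's (20/60 = 0.333/h, against 20/50 = 0.4/h for the metabolite), so λz = 0.333/h. The last two columns give Dose/AUC_m with the dose left in parent mass units.

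| fm | Dose/AUC_m (L/h), true CL_m 20 | Dose/(λz·AUC_m) (L), true V_m 50 | ×1.05 (L/h) | ×1.42 (L/h) |
|---|---|---|---|---|
| 0.05 | 400 | 1200 | 420 | 568 |
| 0.1 | 200 | 600 | 210 | 284 |
| 0.2 | 100 | 300 | 105 | 142 |
| 0.5 | 40 | 120 | 42 | 56.8 |
| 1.0 | 20 | 60 | 21 | 28.4 |

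The same true clearance of 20 L/h gives anything from 20 to 400 L/h, depending only on fm. The volume is wrong even at fm = 1 (60 against 50 L), because in this example the terminal slope belongs to the parent.

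**3. Mass units.** SAP 8.7.4 gives correction factors of 1.05 (TRN-001021) and 1.42 (TRN-001744) for the metabolite-to-parent ratios. Read as parent over metabolite molecular weight, they are also the inflation of Dose/AUC_m when the dose stays in parent mass.

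**4. Illustration from the first-in-human study.** Protocol 2.2.2: "Median TRN-001021 AUC was <10% and 13.7% of the total plasma AUC associated with TERN-201 in the 4 mg and 10 mg groups", respectively. For TRN-001744 the shares were 11.5% at 4 mg and below 10% at 10 mg. The dose cancels, so the metabolite-to-parent ratio of Dose/AUC is AUC_p/AUC_m. Treat the medians as additive and take the other metabolite's share as 0 to 10%:

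- TRN-001021, 10 mg: (100 − 13.7 − 10)/13.7 = 5.57 to (100 − 13.7)/13.7 = 6.30.
- TRN-001744, 4 mg: (100 − 11.5 − 10)/11.5 = 6.83 to (100 − 11.5)/11.5 = 7.70.
- At a share of exactly 10%: TRN-001744 at 10 mg, (100 − 13.7 − 10)/10 = 7.63; TRN-001021 at 4 mg, (100 − 11.5 − 10)/10 = 7.85. Smaller shares give larger ratios.

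On these figures the TRN-001021 ratio would fall from above about 7.85 at 4 mg to about 5.6 to 6.3 at 10 mg. Nothing in the calculation shows whether formation or elimination changed.

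**The case against.** Table 6 calls these quantities apparent and writes them over F. Oral clearance of the parent already carries an unknown bioavailability, so a metabolite value carrying an unknown fraction formed is arguably the same kind of quantity. This stands in part. CL_m/(F·fm) is a legitimate apparent quantity in clearance units, and relabelling would cure the defect as well as deletion would. A reader might infer that the values are meaningless or invalid, and the derivation does not support that. What remains is that one label covers two different quantities in adjacent tables, with the dose in the wrong mass units for the metabolite.

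The plan also gives some protection. Half-life and molecular-weight-corrected metabolite-to-parent ratios are tabulated alongside, so a careful reader could see that exposure is low. SAP 8.7.4.3 withholds values without at least three terminal points, an adjusted r² of at least 0.80 and a negative slope. It leaves CL/F and Vz/F out of the summaries when extrapolation exceeds 30%. These rules reduce the number of values shown, by an unknown amount, but any value that passes is still mislabelled.

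A reader might also take 5.6 as a minimum, or as the size of the error. It is neither. It is a parent-to-metabolite AUC ratio built from medians, which need not add up, in healthy participants, with the mass or molar basis of the shares unstated. The error in metabolite clearance depends on F·fm, which the documents do not give.

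**Conclusion.** The point holds as a mislabelled result that follows from a stated rule. Read as written, Table 6 yields CL_m/(F·fm), and a volume analogue, under names that do not describe them. That Dose means the TERN-201 dose is an inference, but no other dose exists. The size of the departure from true metabolite clearance cannot be computed from the documents; the 5.6 to 6.3 range only shows how far apart the parent and metabolite columns could look.

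The consequence is minor. Metabolite PK is exploratory and summarised descriptively, in a sub-study that SAP 2.2 puts at about 8 active patients in Part 1 and 6 per dose in Part 2. The primary safety endpoint, parent PK, PD, and the exposure-response metrics in SAP 8.9 (AUCtau, Cmax, Ctau) do not depend on these rows.

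**What to change.** Add one sentence to SAP 8.7.4, or a footnote to Table 6: CL/F, CLss/F, Vz/F and Vss/F are calculated for TERN-201 only. Make the parameter list in SAP 8.7.4.3 match.

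If the sponsor prefers to keep the values for the metabolites, label them CL_m/(F·fm) and V_m/(F·fm), and use the dose in molar equivalents (on the reading above, dose divided by 1.05 or 1.42). Add a note that the volume label is correct only where the terminal slope is the metabolite's own.

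Nothing else should be removed. The remaining Table 6 parameters do not use Dose and are sound for the metabolites, including Ctau, which the planned Ctau ratio needs, and the accumulation ratios. The molecular-weight-corrected metabolite-to-parent ratios also stay. The cost is one sentence and four fewer derived parameters per metabolite, with no change to sampling or data collection.
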